3.4.5 Vital Signs

Blood pressure and pulse rate will be measured in the supine position after the patient has rested comfortably as per the schedule of events.

The change from Baseline to each subsequent assessment will be derived for each vital signs parameter.

3.4.6 Weight

Patient's weight will be recorded as per the schedule of events.

Changes from Baseline to each post baseline assessment will be derived.

3.4.7 ECG

Routine ECG will be performed at entry and then annually during the study. The following ECG parameters will be recorded in the eCRF:

- Heart rate (beats/min)
- PR interval (msec)

- QRS duration (msec)
- QT interval (msec)
- QTc interval (msec)
- RR interval (msec)
- Overall interpretation

Interpretation of the ECG will be performed by the investigator and reported as normal, abnormal, inderminate, and if deemed abnormal, whether the abnormality is clinically significant or not clinically significant.

Changes in each ECG parameter from Baseline or any additional unscheduled ECGs, will be derived.

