5.7.4 Cardiac Safety

Routine ECG should be performed at entry and then annually during the study. The ECG traces (*using Limb lead or 12 lead ECG depending on what is available at site*) will be reviewed, signed, and dated by a physician and he/she will record on the trace whether the ECG is normal or abnormal and if deemed abnormal, whether the abnormality is clinically significant (CS) or not clinically significant (NCS).

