If ECG, vital signs, Pregnancy testing and MAVE are done on the same day as the end of study visit for the previous study as the entry day for the long term safety study, then these procedures do not need to be repeated again.

Note: laboratory results can only be used if they are from the same reference laboratory in both studies.

aHUS Parameters

If done within 14 days of entry:

- Thrombotic Markers (D-dimer, prothombin f1/f2)
- Pro-inflammatory Markers (platelet E and P-selectin, CRP (high-sensitivity))
- Haemolytic Markers (Haptoglobin)
- Schistocyte count
- Dialysis Assessment & Plasma Transfer record

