9.1 Statistical methods

A Statistical Analysis Plan (SAP) is in place. There will be no formal statistical inferences. All the study data will be analysed descriptively. Standard summary statistics will be produced for observed values, and changes from entry (where applicable) at the relevant post-entry timepoint.

For continuous variables, these statistics will include the number of patients with available data, mean, standard deviation, median, minimum, maximum. For categorical variables, these statistics will consist of patient counts and associated percentages. Unless otherwise specified, missing data will not be included in the denominator for percentage calculation. Time to event data will be summarised using graphs and summary statistics from the Kaplan-Meier method.

Listings will also be used to display data at the individual patient's level.

Data will be reported at each 3-month time point since the start of the study (where applicable) and over the entire period of the study (where applicable).

Results will be reported for all patients and then separately for PNH and aHUS patients.

- The incidence of AEs, and serious adverse events (SAEs) will be summarised over time for all patients.
- Vital signs, results of standard laboratory tests (clinical chemistry, haematology and urinalysis), and results of limb lead or 12 lead electrocardiograms (ECGs) will be summarised over time for all patients.
- The proportion of subjects with no adverse change in overall scores of Quality of Life using the EORTC QLQ-C30 (some PNH patients only), the EQ-5D-5L and FACIT-F instruments will be summarised over-time.

For PNH patients, additional summaries will include :

- The proportion of subjects with thrombotic and haemolytic event-free status
- The time to thrombotic or haemolytic event since entry.
- The time to first transfusion since entry.
- The proportion of subjects with serum Lactate Dehydrogenase (LDH) <1.8, >1.8 to 2.4, >2.4 to 3, and >3 times the upper limit of normal (ULN).

- The proportion of subjects with median serum Lactate Dehydrogenase (LDH) <1.8, >1.8 to 2.4, >2.4 to 3, and >3 times the upper limit of normal (ULN).
- The proportion of subjects who require PRBC transfusion.
- The proportion of transfusion independent subjects, with haemoglobin (g/L) above the baseline haemoglobin value they had at the start of the parent trial.

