4.12.4 Electrocardiogram

The number and percentage of patients who have an ECG post-baseline Overall interpretation that falls within each category ('Normal'; 'Abnormal, Not Clinically Significant'; 'Abnormal, Clinically Significant') will be tabulated.

Observed values and change from baseline of ECG measurements will be summarised at each applicable study visit.

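### SAP 3.4.7 names no QTc correction formula, so the QTc summaries may mix formulas between sites and, where a machine or formula changes, within patients

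*SAP*

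**What the plan says.** ECG results are one component of the primary safety endpoint (Protocol 3.2.1, SAP 2.4.1). ECGs are taken at entry and then annually, in a multi-centre study lasting up to 4 years.

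SAP 3.4.7 has heart rate, PR, QRS, QT, QTc and RR recorded in the eCRF. QTc appears as "QTc interval (msec" and RR as "RR interval (msec". The only derivation is this: "Changes in each ECG parameter from Baseline or any additional unscheduled ECGs, will be derived". SAP 4.12.4 then states: "Observed values and change from baseline of ECG measurements will be summarised at each applicable study visit". Table 14.3.4.1 presents this for the Full Analysis Set.

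On equipment, Protocol 5.7.4 says "using Limb lead or 12 lead ECG depending on what is available at site". Protocol 9.1 treats both kinds of recording together: "results of limb lead or 12 lead electrocardiograms (ECGs) will be summarised over time for all patients".

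Neither document names a correction formula, computes QTc from QT and RR, provides central reading, or asks for the same machine across visits. The general data handling rules (SAP 4.5) and the changes from protocol (SAP 4.1) do not mention QTc.

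**The concern.** QTc is not measured directly. It is QT adjusted for heart rate, and its value depends on the formula used. A summary of recorded QTc across sites has one meaning only if every record used the same formula, and a change from baseline only if a patient's two records did.

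The plan secures neither. Different machines may apply different corrections, and a site may replace its machine during the study. The study has no control arm, so nothing in the design offsets a measurement artefact that drifts over time. Even with one formula throughout, Bazett leaves a dependence on heart rate.

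The SAP applies the relevant principle elsewhere. In 3.3.2 it expresses LDH as a ratio to the local upper limit of normal so that local laboratories can be compared. QTc gets no such step, although the inputs for one are collected.

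At stake is whether the QTc rows of Table 14.3.4.1 can be read as drug safety information.

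**Working it through.** The plan states no QTc figure, threshold or power, so there is nothing to reproduce. The check asks how large the effect of mixing formulas could be.

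**Inputs.** From the documents: QT, RR and heart rate are recorded (SAP 3.4.7), and the sample is approximately 50 (Protocol 9.2). Assumed, not in the documents: Fridericia QTc of 400 ms (420 ms as a check), heart rates of 50 to 100 beats/min, and the number of patients whose formula changes.

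**Formulas**, with RR in seconds = 60/HR:
- Bazett: QTcB = QT / RR^(1/2)
- Fridericia: QTcF = QT / RR^(1/3)
- Hence, on one tracing, QTcB - QTcF = QTcF × (RR^(-1/6) - 1)

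**Step 1: same tracing, two formulas, QTcF = 400 ms.**

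| HR (beats/min) | RR (s) | QT (ms) | QTcB (ms) | QTcB - QTcF (ms) |
|---|---|---|---|---|
| 50 | 1.200 | 425.1 | 388.0 | -12.0 |
| 60 | 1.000 | 400.0 | 400.0 | 0.0 |
| 75 | 0.800 | 371.3 | 415.2 | +15.2 |
| 90 | 0.667 | 349.4 | 428.0 | +28.0 |
| 100 | 0.600 | 337.4 | 435.5 | +35.5 |

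At QTcF 420 ms the range is -12.6 to +37.3 ms. The sign depends on heart rate, and the size depends on Bazett being one of the formulas. At QTcF 400 ms over the same heart rates, Framingham (QT + 154(1 - RR)) and Hodges (QT + 1.75(HR - 60)) stay within about 8 ms of Fridericia.

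**Step 2: one patient whose formula changes, no true change.** Fridericia at entry and Bazett later, at 75 beats/min: 415.2 - 400.0 = +15.2 ms. Bazett at 90 beats/min at entry and Fridericia later: 400.0 - 428.0 = -28.0 ms.

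**Step 3: effect on the pooled mean change.** If k of 50 patients switch from Fridericia to Bazett at 75 beats/min, the mean moves by (k/50) × 15.16 ms:
- k = 5: 0.10 × 15.16 = 1.5 ms
- k = 10: 0.20 × 15.16 = 3.0 ms
- k = 25: 0.50 × 15.16 = 7.6 ms

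**Step 4: Bazett at both visits, QTcF unchanged, heart rate changes.** From 70 to 80 beats/min: 419.6 - 410.4 = +9.2 ms. From 70 to 90: 428.0 - 410.4 = +17.6 ms. The reverse changes have the opposite sign.

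**Step 5: one Fridericia derivation for all records.** The apparent change is 0 ms in every scenario above. That follows from holding QTcF constant. It measures the discrepancy between formulas and does not show that Fridericia is free of bias.

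**The case against.** The strongest reply is that the documents do not show any formula changing. Lead type follows site equipment, so it varies mainly between sites, whereas change from baseline is taken within patient. With the same machine and formula at both visits, the offset largely cancels. This stands, and it limits the concern about change to patients whose machine or formula does change, plus the heart-rate effect if the formula is Bazett. It does not protect the observed values, which are pooled across sites.

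A reader might infer that QTc is simply each machine's printout. The documents do not say so. That is a reading of their silence, and the stand-alone derived database specification mentioned in SAP section 6 could still name a formula. A derivation for a primary-endpoint component nevertheless belongs in the SAP.

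A reader might also see the carry-over of parent-trial ECGs as a likely source of a switch. Protocol 5.8 permits it "If ECG, vital signs, Pregnancy testing and MAVE are done on the same day as the end of study visit" and the entry day coincide, so one tracing serves both visits. Note vii to Protocol Tables 8 and 9 allows 14 days instead, and the two rules should be reconciled. Neither gives a reason to expect a different machine.

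Nor do the documents predict that heart rate will shift as anaemia changes. Patients are expected to enter on a stable dose, with clinical benefit and sustained complement inhibition.

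Finally, little depends on QTc formally. The analysis is descriptive, there is no QTc decision rule, and the investigator's overall interpretation is tabulated separately. Heart rate, QT and RR are summarised beside QTc and listed by patient, so a reader could see a heart-rate shift and a common QTc could be computed later. All of this stands and keeps the point minor. It also shows that the correction is available from data already planned.

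**Conclusion.** The point holds as a minor gap in specification. The SAP summarises a formula-dependent quantity without fixing the formula, in a study where equipment may differ between sites and over time.

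The stronger reading, that QTc change in this trial will be an artefact of 15 to 36 ms, is not supported. Those figures apply to a single tracing or to a patient whose formula switches, at assumed heart rates of 75 to 100 beats/min. The difference is zero at 60 and negative at 50. In the pooled mean change the effect is about 1.5 to 7.6 ms if 5 to 25 of 50 patients switch at 75 beats/min, and about zero if none do and heart rate is steady. The number of switches, the formulas in use and the heart rates are all unknown from the documents. The mechanism does not depend on them; the size does.

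No effect of lead type itself has been quantified, because the documents give no figure for it.

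**What to change.** In SAP 3.4.7, derive QTcF = QT / RR^(1/3) for every ECG, including the one that serves as baseline. RR is recorded in milliseconds, so divide it by 1000 first. Where RR is missing, use 60/HR. Base the QTc summaries in SAP 4.12.4 and Table 14.3.4.1 on this value, and show the recorded QTc in Listing 16.2.9.2 only.

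The cost is one derivation from data already collected, with no new patient procedure. The downside is that ECGs without QT, or without both RR and heart rate, drop out of the QTcF summary. If the baseline ECG is among them, that patient has no QTcF change from baseline.

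A field for lead set, a sensitivity summary restricted to the same lead set, and counts by QTcF category are optional additions. This point does not depend on them.

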3.4.8 Anti-drug Antibodies (ADA)

Serum samples will be analysed for ADA formation to rVA576 (Coversin) as per the schedule of events. ADA analyses may be performed at a later stage and results reported separately from the main CSR.

3.4.9 Physical Examination

A physical examination, covering the following aspects, will be performed as per the schedule of events:

- General appearance
- Dermatological/skin
- Haematologic/lymphatic
- Heart/cardiovascular
- Respiratory
- Vein and injection site inspection

No derivations will be performed on this data. This data will only be listed.

3.4.10 Pharmacokinetic Coversin Levels

A blood sample for unbound rVA576 Coversin levels will be collected as per the schedule of events.

Unbound nomacopan, total C5 and serum LTB4 levels will be summarised overtime and spaghetti plot of concentrations through time will be produced.

Additional exploratory figures may be produced in order to investigate threshold levels that should be exceeded to ensure >90% inhibition of terminal complement activity. Additional PK analyses may be performed at a later stage and results reported separately from the main CSR.

3.4.11 Fluorescein-labelled proaerolysin FLAER / Flow Cytometry

A blood sample will be collected for flow cytometry measurements at study entry, Month 3, 15, 24, 33 and 48. The following parameters will be evaluated at each clinical site's local laboratory:

- Red blood cells and neutrophils: % cells negative for CD55, CD59, and both CD55 and CD59 and/or

- Granulocytes: % cells negative for CD24, CD16, CD24 and FLAER, CD16 and FLAER and/or
- Granulocytes, monocytes: % cells negative for FLAER and/or Monocytes: % cells negative for CD14, and both CD14 and FLAER

No derivations will be performed on this data. This data will only be listed.

3.5 Compliance and Exposure

Exposure will be derived as the number of days between the first and last dose of study medication in this study.

Study medication compliance will be derived as the proportion of doses that the patient received during the exposure period.

The overall patient compliance (%) will be derived as:

$$= 1 - (\text{Total number of missed doses} / \text{Total number of planned doses})$$

This derived compliance will be categorised:

- <95%
- 95% to <99%
- 99% to 100%
- >100%

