3.1. Trial purpose & Objectives

The objective of the trial is to provide a database of information regarding long-term administration of rVA576 (Coversin) to show that it remains safe for long periods and is

[REDACTED]

acceptable to patients and show that the effect observed in the previous clinical trial is maintained. It also provides the opportunity to adjust an individual patient's dose or dose frequency should it be considered desirable. All patients enrolled into the CONSERVE study will have transitioned from a parent clinical trial.

The specific objectives of the study are:

- To observe the long term safety and efficacy of rVA576 (Coversin) in a period exceeding the 6 months of treatment.
- To assess the long term patient acceptability of rVA576 (Coversin) using the EORTC QLQ-C30 (for some PNH only), EQ-5D-5L & FACIT-F (both PNH & aHUS) instruments and the Sponsor non validated questionnaire.
- To observe the changes, if any, in the production of anti-drug antibodies (ADA) and whether such antibodies are, or become, neutralising

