5.10 Missed doses

For PNH patients:

For a missed dose of more than >24 hours, the sample for PD (CH50) analysis should be taken if possible just prior to the next morning dose of rVA576 (Coversin). As the CH50 results will not be available for some days the Investigator should be guided by the history, clinical signs or platelet count and LDH. In some cases, the PI may feel that an ablating dose is not required and the patient should resume their usual dosing schedule as soon as possible. In PNH, clinical signs of intravascular haemolysis following resumption of dosing mandates re-initiation of the AD schedule. The CRO and the Sponsor should be informed as soon as possible.

Dose	Interval	Missed Dose <4hr	Missed Dose <24hrs	Missed dose by day(s)>24hrs
15mg	12 hourly	Dose to be taken as soon as patient realizes	Take 15mg dose immediately and 15mg dose at usual time	Take ablating dose 60mg/30mg. then take dose as per usual routine
22.5mg	12 hourly		Take 22.5mg dose immediately and 22.5 mg dose at usual time	
30mg	12 hourly		Take 30mg dose immediately and 30mg dose at usual time	
30mg	24 hourly		Take 45mg dose immediately and 45mg dose at usual time	
45mg	24 hourly		Take 45mg dose immediately and 45mg dose at usual time	

For aHUS patients:

In the event of one missed dose (defined as a dose not taken within a one-hour time window either side of the specified time) the following procedure should be adopted by the patient:

- Take the appropriate dose as per the day of the protocol as soon as possible and then resume the usual dosing schedule at the specified times

In the event of more than one missed dose the CRO and the Investigator's clinic should be informed as soon as possible and the following procedure should be adopted:

- Take 60 mg Coversin followed by 30 mg 12 hours later and then resume the usual dosing schedule (i.e. between 07:00 and 11:00 hrs daily) at the first time point after the ablation doses.

The Investigator's clinical staff should arrange for a Central laboratory blood draw for PK/PD to be taken 3 days \pm 1 day after first becoming aware of the missed doses in this situation.

The sample for PD (CH50) analysis should be taken just prior to dosing with rVA576 (Coversin).

As the CH50 results are unlikely to be available for some days the Investigator should be guided by the history, clinical signs or platelet count and LDH as to whether it is necessary to administer additional Ablating Doses.

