6.4 Compliance

Reasonable levels of compliance are assumed as a condition of entry (prior enrolment in and completion of a rVA576 (Coversin) clinical trial). As a measure of compliance, all empty rVA576 (Coversin) vials will be returned to the clinical unit and diary cards

will be reviewed by research staff. At the end of the study, all unused vials will be returned to the Sponsor or representative or destroyed at site.

In addition to the above measures, clinic staff may call the patient's home or set up an automated text message reminder according to the subjects dosing schedule.

Example text as follows: "A gentle reminder - please administer your medicine this morning/evening and record the time, dose and location of injection in the Patient Dosing Diary.

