6.5 Interruption of Treatment

If treatment is interrupted, either for reasons outside the patient's or the investigator's control or because it is considered to be in the patient's best interest it may be resumed at the discretion of the investigator and Sponsor. Any interruption of >24 hours will require an ablating regimen of 60mg followed by 30mg 12 hours later before resuming normal dosing, this should be discussed with the Sponsor. In the event of an interruption of treatment of >28 days, the investigator should discuss with the Sponsor the advisability of resuming treatment.

7 Safety Reporting

All AEs occurring from the signing of the voluntary Informed Consent Form (ICF) to the end of the trial visit will be recorded. All adverse events, whether or not considered to be related to the study drug, will be monitored and reported at all stages of the study. Adverse events occurring between clinic visits will be reported by the patient or recorded at the next clinic visit and entered on the adverse event form of the case report forms. All adverse events must be fully recorded in the patient notes throughout the entire study period and will be transcribed into the subject's eCRF.

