4.9 Study Drug Exposure and Compliance

Exposure to study medication, defined as the number of days between first and last dose (see section 3.5), will be summarized using descriptive statistics. In addition, a table will be provided to display the number and percentage of patients with exposure in the following categories:

- 1-182 days
- 183-365 days
- 366-730 days
- 731-1095 days

Study medication percentage compliance will be summarised using descriptive statistics. The count and percentage of patients with overall compliance will also be tabulated:

- <95%
- 95% to <99%

- 99% to 100%
- >100%

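### The SAP's compliance formula cannot exceed 100%, so the tabulated category above 100% is always empty and extra doses never register (minor)

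*SAP*

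**What the plan says.** SAP section 3.5 gives a verbal definition, "Study medication compliance will be derived as the proportion of doses that the patient received during the exposure period", followed by a formula: one minus the ratio of missed to planned doses. The result is labelled as a percentage, but the formula has no factor of 100. It is then grouped as below 95%, 95% to below 99%, 99% to 100%, and above 100%. SAP section 4.9 repeats the four groups for reporting: "The count and percentage of patients with overall compliance will also be tabulated". The output is Table 14.3.7. Exposure carries no amount of drug either: "Exposure will be derived as the number of days between the first and last dose of study medication in this study".

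Three features of the protocol bear on this.

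- The planned regimen can change within a patient (section 3.1): "It also provides the opportunity to adjust an individual patient's dose or dose frequency should it be considered desirable".
- Some doses are directed outside the usual regimen. Section 6.5 says: "Any interruption of >24 hours will require an ablating regimen of 60mg followed by 30mg 12 hours later before resuming normal dosing". For PNH patients with a gap of more than 24 hours, the section 5.10 table says: "Take ablating dose 60mg/30mg. then take dose as per usual routine".
- Section 6.4 has a sample reminder that asks patients to "record the time, dose and location of injection in the Patient Dosing Diary".

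The SAP does not define a missed dose. Protocol section 5.10 defines one for aHUS patients, whom the SAP no longer covers. For PNH patients it gives only actions by length of delay.

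**The concern.** The formula and its categories contradict each other. A band above 100% makes sense only if the measure can register more doses than planned, and this one has no term for them. A reader of Table 14.3.7 would take a zero in that row as evidence that nobody took extra doses, when the zero is fixed by the formula.

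A related limit is that the measure counts injections and not milligrams. Patients prepare their own doses, dose levels differ between and within patients, and no cumulative-dose table is planned. A dose of the wrong size therefore counts the same as a correct one.

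**Working it through.** **Inputs.** The formula and bands come from SAP 3.5 and 4.9, the dose levels from the protocol's dose decision table (section 5.2), and the overdose threshold of 90 mg in 24 hours from protocol 7.2.3. Planned doses P = 2 × 365 = 730 is an assumption (12-hourly for one year). The upper bound does not depend on it.

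**Upper bound.** Let M be the number of missed doses, from 0 to P. The SAP value is 100 × (1 − M/P).

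- M = 0 gives 100.0%; M = 730 gives 0%.
- Of the 731 possible values with P = 730, none exceeds 100%.
- The maximum is also 100.0% for P = 365, 1460 and 2922.

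The band above 100% cannot be reached by the formula as written. The verbal definition, read as a proportion, has the same ceiling.

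**Three measures compared.** P = 730, planned dose 22.5 mg 12-hourly. The milligram figures illustrate the arithmetic and suggest no dose.

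| Patient | SAP: 100 × (1 − M/P) | 100 × taken/planned | 100 × mg taken/mg planned |
|---|---|---|---|
| None missed, 73 extra | 100.0 | 803/730 = 110.0 | 110.0 |
| 10 missed, none extra | 1 − 10/730 = 98.6 | 720/730 = 98.6 | 98.6 |
| 10 missed, 10 extra | 98.6 | 730/730 = 100.0 | 100.0 |
| Every dose 15 mg | 100.0 | 100.0 | 15/22.5 = 66.7 |
| Every dose 30 mg | 100.0 | 100.0 | 30/22.5 = 133.3 |

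Row 1 shows that extra doses do not register in the SAP measure. Row 3 shows the cost of a simple ratio: extra doses offset missed ones, so missed doses need their own line. Rows 4 and 5 show that no dose count detects wrong-sized doses. Row 5 is 2 × 30 = 60 mg in 24 hours, below the overdose threshold.

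**Ablating doses.** Take 22.5 mg 12-hourly for 30 days, so 60 slots, with 3 missed and one ablating regimen of two injections. If those two fill scheduled slots, 60 − 3 − 2 = 55 ordinary doses were taken.

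- SAP formula: 1 − 3/60 = 95.0%.
- Ablating doses left out of the numerator, slots kept in the denominator: 55/60 = 91.7%. The patient is marked down for following the protocol.
- Slots removed from both: 55/(60 − 2) = 55/58 = 94.8%, that is, 3 missed of 58 ordinary doses.

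If instead the ablating doses fill no scheduled slot, 57 ordinary doses were taken. Counting the two as extra doses gives 59/60 = 98.3%; leaving them out gives 57/60 = 95.0%. The SAP has to state the rule, since the answer moves between 91.7% and 98.3% with it.

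**The case against.** The band could be reached if a programmer set missed doses to planned minus taken and let it go negative: 1 − (730 − 803)/730 = 110.0%. The SAP does not say so, and a missed dose is naturally a count. This shows what was probably intended, and that two programmers could fill the table differently.

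Dose-count compliance is a legitimate choice, and little hangs on it here. The study is descriptive, there is one Full Analysis Set, and compliance defines no population or endpoint. Exposure, compliance and drug accountability are listed per patient, and unbound drug and CH50 are summarised over time. All of this stands. The missing milligram term is a limit of the measure, not an error.

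Stronger readings are tempting, and the documents do not support them:

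- *Over-dosing goes unreported.* Protocol 7.2.3 requires every overdose, defined as 90 mg or above in 24 hours, to be reported as an adverse event with or without symptoms. Doubling 22.5 mg 12-hourly is 2 × 45 = 90 mg and is caught there. Only smaller excesses and under-sized doses appear in no planned summary.
- *Dose-increase decisions would be misled.* The check for poor compliance in protocol 5.9 is made by the investigator for one patient at a time, and section 6.4 provides returned vials and diaries for it. Table 14.3.7 plays no part.
- *Protocol-directed ablating doses push true compliance above 100%.* That follows only if they are counted as extra to the regimen. On other counts the example above gives 91.7% to 95.0%.
- *Patients with extra or wrong-sized doses are shown as fully compliant.* This is exact only when no dose is missed. Otherwise the value stays at its missed-dose level, such as 98.6% in row 3.

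**Conclusion.** The SAP's rule is wrong as written: its top category cannot be filled, extra doses have no effect on the value, and the factor of 100 is missing. This rests on missed doses being a non-negative count and holds for any number of planned doses. The consequence is confined to the compliance part of Table 14.3.7, where a zero in the top row would carry no information. How many patients would fall there under a corrected measure cannot be known from the documents; the 110.0%, 66.7% and 133.3% are illustrations. Severity is minor.

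**What to change.** In SAP 3.5:

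1. Define compliance as 100 × (doses taken / doses planned under the regimen in force on each day), allow values above 100%, and keep the four bands.
2. Define a missed dose for PNH patients, and report missed doses on a separate line so that extra doses do not offset them.
3. Report ablating doses as their own count, and remove the slots they occupy from both numerator and denominator.
4. If the dose recorded in the diary is captured in the eCRF, add a second line of mg taken over mg prescribed. Neither document states that it is captured, and the diary instruction comes from a sample reminder text, so the sponsor should confirm this first.

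Items 1 to 3 need SAP wording and one revised derivation, with no change for patients or visits, provided extra and ablating doses are identifiable in the database. The downside is a little more programming, and some patients will show values above 100%. Deleting the top band would also remove the contradiction at almost no cost, but extra doses would still go unseen in the table.
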